## **10.0 TRIAL PROCEDURES**

### **10.1 Trial Procedures**

The Trial Flow Chart - Section 9.0 summarizes the trial procedures to be performed at each visit. Individual trial procedures are described in detail below. It may be necessary to perform these procedures at unscheduled time points if deemed clinically necessary by the investigator.

Furthermore, additional evaluations/testing may be deemed necessary by the Sponsor and/or Merck for reasons related to subject safety. In some cases, such evaluation/testing may be potentially sensitive in nature (e.g., HIV, Hepatitis C, etc.), and thus local regulations may require that additional informed consent be obtained from the subject. In these cases, such evaluations/testing will be performed in accordance with those regulations.

#### **10.1.1 Administrative Procedures**

##### **10.1.1.1 Informed Consent**

The Investigator must obtain documented consent from each potential subject prior to participating in a clinical trial.

###### **10.1.1.1.1 General Informed Consent**

Consent must be documented by the subject's dated signature or by the subject's legally acceptable representative's dated signature on a consent form along with the dated signature of the person conducting the consent discussion. A remote consent can be obtained if the subject lives >50 miles from the treatment site. The informed consent document can be sent by facsimile and/or through a secure email account. The consent interview can be performed by telephone and a signed consent form can be returned to the clinical investigator by facsimile and/or through a secure email account to protect the confidentiality of the subject. The patient must be re-consented in person prior to starting treatment.

A copy of the signed and dated consent form should be given to the subject before participation in the trial.

The initial informed consent form, any subsequent revised written informed consent form and any written information provided to the subject must receive the IRB/ERC's approval/favorable opinion in advance of use. The subject or his/her legally acceptable representative should be informed in a timely manner if new information becomes available that may be relevant to the subject's willingness to continue participation in the trial. The communication of this information will be provided and documented via a revised consent form or addendum to the original consent form that captures the subject's dated signature or by the subject's legally acceptable representative's dated signature.

Specifics about a trial and the trial population will be added to the consent form template at the protocol level.

---

*CONFIDENTIAL*

*This document is confidential. Do not disclose or use unless authorized.*

The informed consent will adhere to IRB/ERC requirements, applicable laws and regulations and Sponsor requirements.

#### **10.1.1.2 Inclusion/Exclusion Criteria**

All inclusion and exclusion criteria will be reviewed by the treating investigator or qualified designee to ensure that the subject qualifies for the trial.

#### **10.1.1.3 Medical History**

A medical history will be obtained by the treating investigator or qualified designee. Medical history will include all active conditions, and any condition diagnosed within the prior 10 years that are considered to be clinically significant by the Investigator. Details regarding the disease for which the subject has enrolled in this study will be recorded separately and not listed as medical history.

#### **10.1.1.4 Prior Medications Review**

The treating investigator or qualified designee will review prior medication use, including any protocol-specified washout requirement, and record prior medication taken by the subject within 28 days before starting the trial. Treatment for the disease for which the subject has enrolled in this study will be recorded separately and not listed as a prior medication.

#### **10.1.1.5 Concomitant Medications Reviews**

The treating investigator or qualified designee will record medication, if any, taken by the subject during the trial. All medications related to reportable SAEs and ECIs should be recorded as defined in Section 11.0.

#### **10.1.1.6 Disease Details**

The treating investigator or qualified designee will obtain prior and current details regarding disease status.

#### **10.1.1.7 Prior Treatment Details**

The treating investigator or qualified designee will review all prior treatments including systemic and intralesional treatments, radiation and surgeries.

#### **10.1.1.8 Subsequent Therapy Status**

The treating investigator or qualified designee will review all new surgical, systemic and intralesional therapy initiated after the last dose of trial treatment. If a subject initiates a new therapy within 30 days after the last dose of trial treatment, the 30 day Safety Follow-up visit must occur before the first dose of the new therapy. Once new therapy has been initiated the subject will move into survival follow-up.

---

*CONFIDENTIAL*

*This document is confidential. Do not disclose or use unless authorized.*

#### **10.1.1.9 Assignment of Screening Number**

All consented subjects will be given a unique screening number that will be used to identify the subject for all procedures that occur prior to randomization or treatment allocation. Each subject will be assigned only one screening number. Screening numbers must not be re-used for different subjects. Any subject who is screened multiple times will retain the original screening number assigned at the initial screening visit.

#### **10.1.1.10 Assignment of Randomization Number**

All eligible subjects will be allocated, by non-random assignment, to trial treatment and will receive a unique number. This unique number is termed a randomization number throughout the protocol for operational purposes. The randomization number identifies the subject for all procedures occurring after treatment allocation. Once a randomization number is assigned to a subject, it can never be re-assigned to another subject.

A single subject cannot be assigned more than 1 unique number.

#### **10.1.1.11 Trial Compliance (Medication/Diet/Activity/Other)**

Any interruptions from the protocol specified treatment plan due to toxicity will result in the patient withdrawing from treatment.

Administration of trial medication will be witnessed by the investigator and/or trial staff. The total volume of trial treatment infused will be compared to the total volume prepared to determine compliance with each dose administered.

### **10.1.2 Clinical Procedures/Assessments**

#### **10.1.2.1 Adverse Event (AE) Monitoring and Rapid Review Overview**

The treating investigator or qualified designee will assess each subject to evaluate for potential new or worsening AEs as specified in the Trial Flow Chart and more frequently if clinically indicated. Adverse experiences will be graded and recorded throughout the study and during the follow-up period according to NCI CTCAE Version 4.0. Toxicities will be characterized in terms regarding causality, toxicity grading, and action taken with regard to trial treatment.

For subjects receiving treatment with pembrolizumab all AEs of unknown etiology associated with pembrolizumab exposure should be evaluated to determine if it is possibly an event of clinical interest (ECI) of a potentially immunologic etiology (termed immune-related adverse events, or irAEs); see the separate ECI guidance document in Appendix 4 regarding the identification, evaluation and management of potential irAEs.

Please refer to Section 11.0 for detailed information regarding the assessment and recording of AEs.

---

*CONFIDENTIAL*

*This document is confidential. Do not disclose or use unless authorized.*

### **10.1.2.2 Full Physical Exam**

The treating investigator or qualified designee will perform a complete physical exam during the screening period. Clinically significant abnormal findings should be recorded as medical history. A full physical exam should be performed during screening.

### **10.1.2.3 Directed Physical Exam**

For cycles that do not require a full physical exam per the Trial Flow Chart, the treating investigator or qualified designee will perform a directed physical exam as clinically indicated prior to trial treatment administration. Patients will undergo a video-recorded transnasal flexible fiberoptic laryngoscopy and tracheoscopy examination within +/- 24 hours that they receive each dose of pembrolizumab. The treating surgeon will complete the Severity Scoring Sheets (found in Section 18.0A Surgical Scoring sheets) at each session and document procedure findings.

### **10.1.2.4 Vital Signs**

The treating investigator or qualified designee will take vital signs at screening, prior to the administration of each dose of trial treatment and at treatment discontinuation as specified in the Trial Flow Chart (Section 9.0). Vital signs should include temperature, pulse, respiratory rate, weight and blood pressure. Height will be measured at screening only.

### **10.1.2.5 Eastern Cooperative Oncology Group (ECOG) Performance Scale**

The treating investigator or qualified designee will assess ECOG status at screening, prior to the administration of each dose of trial treatment and discontinuation of trial treatment as specified in the Trial Flow Chart.

### **10.1.2.6 Tumor Imaging and Assessment of Disease**

Clinical response rates will be the primary measure for assessment of tumor response and as a basis for all protocol guidelines related to disease status (e.g. discontinuation of study therapy). Clinical response will be assessed by direct visualization and scoring of disease burden within the upper aerodigestive tract (**Appendix A: Surgical Scoring and Appendix G: CRFs**).

The burden of disease will be assessed at each direct laryngoscopy/tracheoscopy examination performed in clinic and in the operating room, and the extent of papilloma growth will be measured using an instrument previously described [8, 9]. Briefly, evaluations will be made of five major anatomic sites in the larynx (epiglottis, false cords, ventricle, true cords, and subglottis), which are subdivided into 23 subsites. Four major anatomic sites in the tracheobronchial tree (trachea, tracheostomy site, if present, carina and mainstem bronchus) are divided into 6 subsites. The rating incorporates three components. Number of sites (AS) is the actual number of affected sites. For laryngeal disease, this value can range from 0 to 23. Surface area (SA) involvement at each major site is rated on the following scale: 0 (none), 1 (under 1/3 of area is affected), 2 (under 2/3 of area), or 3 (more than 2/3 of area). For the total of five major sites this value can range from 0 to 15. Extent of lumen obstruction (LO) reflects the degree of airway obstruction at each site, on a similar scale of 0-3. For the total of five major sites this

---

*CONFIDENTIAL*

*This document is confidential. Do not disclose or use unless authorized.*

value can range from 0 to 15. The three components (AS, SA and LO) are summed to yield a single overall rating, but the scores are entered separately into the computer to permit analysis of separate components of the score if desired. The potential range of this scoring system is 0 to 53 for laryngeal disease; the range observed in previous studies was 0 to 43 ([www.clinicaltrials.gov](http://www.clinicaltrials.gov); NCT00571701). Scores for tracheobronchial disease are calculated similarly. The maximum possible AS score is 6. The maximum SA and LO scores are each 12. Therefore, the maximum summed score for tracheo-bronchial involvement is 30. Copies of the scoring sheet pages are included in the appendix, as part of the case report forms (**Appendix A: Surgical Scoring and Appendix G: CRFs**).

To ensure protocol compliance and consistency among participating sites, a Rapid Review will be conducted. The videos from the screening clinic and operating room visit for each institution's first three cases will be reviewed by [name] and the Site Investigator via a WebEx and Teleconference. Rapid Reviews will be conducted within 14 days of the surgery. Additional reviews may be requested by the Principal Investigator until protocol compliance is adequately demonstrated. Review will be arranged by the Coordinating Center as per procedures listed below:

#### Process for Endoscopic Video and Score Sheet Rapid Review:

1. At the time of registration, the Coordinating Center will identify if the patient is subject to Rapid Review.
2. Coordinating Center is notified of the date and time of the surgery to be reviewed for each case by the external sites. Video and score sheets will be sent per instructions below to the Coordinating Center.
3. Once the video and score sheet are reviewed, the PI and Site Investigator will review the video via a WebEx and teleconference arranged by the Coordinating Center.
4. Any issues identified during the review will be communicated, documented, and resolved at the time of review.
5. The Coordinating Center notifies the study team at the participating site that the review is complete and provides email confirmation to the study team.

De-identified videos of the endoscopic (laryngoscopy, tracheoscopy, and/or bronchoscopy) examination will be sent to the Coordinating Center every 4 cycles (at the time of surgical biopsy). Videos maybe downloaded onto a secure server and/or sent via a USB drive or CD labeled with two patient identifiers to the following address:

MGH CCPO Multi-Center Program  
c/o [name]-Program Manager  
[name]  
Boston, MA 02114

---

CONFIDENTIAL

*This document is confidential. Do not disclose or use unless authorized.*

Severity Scoring sheets should be submitted to the Coordinating Center in real time. PDFs of all sheets should be emailed to [name] at [[contact]](mailto:[contact]) and the MC Coordinator over a secure network. In subject header include study number (15-469) and patient's ID number and initials.

#### **10.1.2.6.1 Assessment of Response**

Overall response rates according to clinical assessment will be derived from time-point response assessments as follows:

- **Complete Response (CR):** Complete disappearance of all tumor lesions (and no new lesions). CR must be confirmed by repeated, consecutive assessments made no less than 4 weeks from the date first documented.
- **Partial Response (PR):** Decrease in the summed score for laryngeal and tracheo-bronchial involvement by 25% or greater by a consecutive assessment at least 4 weeks after first documentation.
- **Stable Disease (SD):** Failure to meet criteria for CR or PR, in absence of PD.
- **Progressive Disease (PD):** At least 25% increase in the summed score for laryngeal and tracheo-bronchial involvement, confirmation by a repeat, consecutive assessment no less than 4 weeks from the date first documented.

3-Dimension tracheal reconstruction with volumetric analysis and RECIST 1.1 will be applied as another measure for assessing tumor response in those patients with tracheal and/or pulmonary involvement, respectively, and will contribute to the basis for all protocol guidelines related to disease status (e.g. discontinuation of study therapy).

For those patients with pulmonary lesions measurable by RECIST 1.1, CT scans of the chest will be obtained every 12 weeks (84 days +/- 7 days) to assess response per RECIST 1.1 criteria. Imaging assessments will be adapted as follows to account for the unique tumor response seen in this class of therapeutics.

At the baseline imaging study, if there is no evidence of pulmonary disease measurable by RECIST 1.1, the patient will be followed with serial laryngoscopy/tracheoscopy examinations every 3 weeks and serial CT scans will be obtained every 6 months until the end of the study. If there is evidence of pulmonary disease, lymphadenopathy, and/or extra-tracheal disease (except those involving the larynx) measurable by RECIST 1.1, the patient will undergo repeat imaging every 12 weeks ( $\pm$  7 days). If two consecutive imaging assessments demonstrate SD or CR, the patient will undergo repeat imaging every 6 months until the end of the study. If imaging shows PD, tumor assessment should be repeated no less than 4 weeks from the date first documented in order to confirm PD with the option of continuing treatment for clinically stable subjects as discussed below in the Table.

Clinically stable is defined by the following criteria:

---

*CONFIDENTIAL*

*This document is confidential. Do not disclose or use unless authorized.*

\*Absence of signs and symptoms indicating disease progression

\* No decline in ECOG performance status

\*Absence of rapid progression of disease

	Clinical Stable		Clinically Unstable	
	Imaging	Treatment	Imaging	Treatment
1 st radiologic evidence of PD	Repeat imaging at $\geq$ 4 weeks to confirm PD	May continue study treatment at the Investigator's discretion while awaiting confirmatory can	Repeat imaging at $>4$ weeks to confirm PD if possible	Discontinue treatment
Repeat scan confirms PD	No additional imaging required	Discontinue treatment	No additional imaging required	N/A
Repeat scan shows SD, PR or CR	Continue imaging assessments	Continue study treatment at the Investigator's discretion	Continue imaging assessments if possible	May restart study treatment if condition has improved and/or clinically stable per Investigator's discretion

In determining whether or not the tumor burden has increased or decreased, all target lesions as well as non-target lesions should be considered. Subjects that are deemed clinically unstable are not required to have repeat imaging for confirmation. If radiologic progression is confirmed, then the subject will be discontinued from trial treatment. If radiologic progression is not confirmed, then the subject should resume/continue trial treatment and have their next scan in 12 weeks (84  $\pm$  7 days).

After the first documentation of progression, it is at the discretion of the investigator to keep a clinically stable subject on trial treatment or to stop trial treatment until repeat imaging performed at least 28 days later confirms progression. When feasible, subjects should not be discontinued until progression is confirmed. Subjects that are deemed clinically unstable are not required to have repeat imaging for confirmation. If progression is confirmed, then the subject will be discontinued from trial treatment. If progression is not confirmed, then the subject should resume/continue trial treatment.

---

*CONFIDENTIAL*

*This document is confidential. Do not disclose or use unless authorized.*

**NOTE:** If a subject with confirmed radiographic progression (i.e. 2 scans at least 28 days apart demonstrating progressive disease) is clinically stable or clinically improved, and there is no further increase in the tumor dimensions at the confirmatory scan, an exception may be considered to continue treatment upon consultation with the Sponsor. Clinically stable subjects should also have at the confirmatory scan no further increase in the target lesions, no unequivocal increase in non-target lesions, and no additional new lesions develop (non-worsening PD) to continue study treatment.

Imaging during the follow-up period is to be repeated every 6 months for subjects who discontinue trial treatment for reasons other than disease progression until the subject experiences confirmed disease progression or starts a new antineoplastic therapy.

Any new pulmonary findings on imaging which are not found to be clinically relevant or associated with RRP will be managed with standard guidelines and risk stratification of solitary pulmonary nodules.

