## 2.0 TRIAL DESIGN

### 2.1 Trial design

This is a non-randomized phase II trial in male and female subjects diagnosed with recurrent respiratory papillomatosis (RRP) with extensive laryngeal, tracheal and/or pulmonary involvement. Approximately 22 subjects will be enrolled in this trial to examine the safety and efficacy in this subject population who would be administered up to 200 mg of pembrolizumab every 3 weeks. Subjects will be evaluated every 3 weeks (21 days  $\pm$  3 days) in the clinic with a video-recorded transnasal flexible laryngoscopy and tracheoscopy examination to assess clinical response on treatment (**Appendix A**) as well as evaluated every 24 weeks (169 days  $\pm$  14 days) with CT scans to assess response per volumetric analysis. For those patients with pulmonary lesions measurable by RECIST 1.1, CT scans of the chest will be obtained every 12 weeks (84 days  $\pm$  7 days) to assess response per RECIST 1.1 criteria. In addition, patients will complete quality of life questionnaires to assess preference of pembrolizumab as compared to standard of care treatment, which is surgery, for this patient population (**Appendix F**).

As part of the natural course of this disease, patients undergo operative procedures for repeated debridement of papillomata within their upper aerodigestive tract in order to improve their breathing and/or voice quality. Prior to starting pembrolizumab, subjects will undergo a comprehensive laryngoscopy and tracheobronchoscopy to map and score their disease burden in the upper aerodigestive tract and a pre-treatment biopsy would be obtained at that time. Subsequently, at a minimum of every 12 weeks (84 days  $\pm$  14 days), subjects will be taken to the operating room for a comprehensive laryngoscopy and tracheobronchoscopy and debridement of any papillomatous lesions which obstructs the caliber of their airway by more than 50% and/or other lesions at the discretion of the surgeon. Some patients will require more frequent visits to the operating room depending on their disease burden and associated clinical symptoms. Biopsies will be obtained during all operative visits.

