The burden of disease will be assessed at each direct laryngoscopy and tracheoscopy examination performed in the clinic and in the operating room, and the extent of papilloma growth will be measured using an instrument previously described [8, 9]. Briefly, evaluations will be made of five major anatomic sites in the larynx (epiglottis, false cords, ventricle, true cords, and subglottis), which are subdivided into 23 subsites. Four major anatomic sites in the tracheo-bronchial tree (trachea, tracheostomy site, if present, carina and mainstem bronchus) are divided into 6 subsites. The rating incorporates three components. Number of sites (AS) is the actual number of affected sites. For laryngeal disease, this value can range from 0 to 23. Surface area (SA) involvement at each major site is rated on the following scale: 0 (none), 1 (under 1/3 of area is affected), 2 (under 2/3 of area), or 3 (more than 2/3 of area). For the total of five major sites this value can range from 0 to 15. Extent of lumen obstruction (LO) reflects the degree of airway obstruction at each site, on a similar scale of 0-3. For the total of five major sites this value can range from 0 to 15. The three components (AS, SA and LO) are summed to yield a single overall rating, but the scores are entered separately into the computer to permit analysis of separate components of the score if desired. The potential range of this scoring system is 0 to 53 for laryngeal disease; the range observed in previous studies was 0 to 43 ([www.clinicaltrials.gov](http://www.clinicaltrials.gov); NCT00571701). Scores for tracheobronchial disease are calculated similarly. The maximum possible AS score is 6. The maximum SA and LO scores are each 12. Therefore, the maximum summed score for tracheo-bronchial involvement is 30. Copies of the scoring sheet pages are included in the appendix, as part of the case report forms.

Overall response rates according to clinical assessment will be derived from time-point response assessments as follows:

- **Complete Response (CR):** Complete disappearance of all tumor lesions (and no new lesions). CR must be confirmed by repeated, consecutive assessments made no less than 4 weeks from the date first documented.
- **Partial Response (PR):** Decrease in the summed score for laryngeal and tracheo-bronchial involvement by 25% or greater by a consecutive assessment at least 4 weeks after first documentation.

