Clinical imaging assessed by laryngoscopy and tracheoscopy will be performed every 3 weeks (21 days $\pm$  3 days). In addition, a comprehensive laryngoscopy, tracheoscopy, and bronchoscopy will be performed every 4 cycles in the operating room.

VHI-10 questionnaire is required only for subjects enrolled after IRB approval and/or activation of Protocol AM 10

After 1 year, the clinical assessment will be reduced to 24 weeks for 12 months only.

*CONFIDENTIAL*

*This document is confidential. Do not disclose or use unless authorized.*

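### The clinical CR/PR rule does not exclude score falls caused by on-treatment debridement, so surgical removal can count as response in the single-arm primary ORR

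*Combined protocol and SAP*

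**What the plan says.** Sections 4.2.3.1 and 10.1.2.6.1 give the same rule. CR is disappearance of all lesions, confirmed no less than 4 weeks later. PR is "Decrease in the summed score for laryngeal and tracheo-bronchial involvement by 25% or greater", shown by a consecutive assessment at least 4 weeks after it is first documented. The score is the plain sum of the number of affected sites (AS), surface area (SA) and lumen obstruction (LO). Section 10.1.2.6 makes clinical response the primary measure of tumor response, and Section 14.1 counts CR/PR by clinical assessment and/or RECIST.

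Scoring is frequent and covers both settings: "The burden of disease will be assessed at each direct laryngoscopy/tracheoscopy examination performed in clinic and in the operating room". Footnote 22 of the Section 9.1 flow chart adds: "Clinical imaging assessed by laryngoscopy and tracheoscopy will be performed every 3 weeks". Section 10.1.2.3 has the surgeon complete the severity sheets at each session.

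Section 2.1 schedules operative visits at least every 12 weeks, more often for some patients, with "debridement of any papillomatous lesions which obstructs the caliber of their airway by more than 50" per cent "and/or other lesions at the discretion of the surgeon". A pre-treatment endoscopy is done "to map and score their disease burden in the upper aerodigestive tract", but the PR rule does not name that score as its reference.

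Section 14.1 stops the trial if 1 or fewer of 11 adults respond and considers further testing if at least 6 of 21 do. It states a 49% chance of early closure and an 8% chance of a positive conclusion at a true rate of 15%, and 86% at 38%.

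**The concern.** Debridement lowers all three score components directly. A patient whose papillomata are removed at a scheduled operation will usually score lower at the next clinic visits whether or not the drug works. The rule asks only whether the score fell and whether the fall lasted 4 weeks. There is no control arm in which the same surgical effect would appear, and few responders are needed (2 of 11, then 6 of 21), so one or two surgical falls counted as PR could change either decision. The 8% in Section 14.1 assumes that a null drug produces responses in 15% of patients. Section 14.1 gives no allowance for responses produced by surgery.

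**Working it through.** **1. The plan's own figures.** Inputs from Section 14.1: stop if at most 1 of 11; positive if at least 6 of 21. With X1 ~ Bin(11, p) and X2 ~ Bin(10, p):

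- P(early stop) = P(X1 ≤ 1). At p = 0.15: 0.85^11 + 11 × 0.15 × 0.85^10 = 0.167 + 0.325 = 0.492 (stated 49%).
- P(positive) = Σ over x from 2 to 11 of P(X1 = x) × P(X2 ≥ 6 − x). At p = 0.15: 0.0793 (stated 8%). At p = 0.38: 0.857 (stated 86%).

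All three reproduce. The gap is in the endpoint that feeds the design, not in the design.

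**2. Does 4-week confirmation filter out surgery?** After an operative visit at week 12, clinic scores fall at weeks 15, 18 and 21, and the next scheduled operation is at week 24. Weeks 15 to 18 are 21 days apart, at most 21 + 3 + 3 = 27 with the ±3-day windows, so week 18 cannot confirm. Weeks 15 to 21 are 42 days apart, at least 42 − 6 = 36, so week 21 can. For patients travelling more than 50 miles the window is ±7 days, and week 18 could be 21 + 14 = 35 days after week 15. Confirmation therefore does not remove a surgical effect that lasts 9 weeks.

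**3. Can one debrided site be enough?** A site scoring AS 2 + SA 2 + LO 2 = 6 meets the threshold, if cleared with no regrowth, for any total up to 6 / 0.25 = 24. If slight regrowth in both subsites brings it back to 2 + 1 + 1 = 4, the retained fall is 2 points, enough only for totals up to 2 / 0.25 = 8. The effect depends heavily on regrowth, for which the documents give no rate.

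**4. Effect on the decision (assumed inputs).** Let s be the share of true non-responders whom surgery turns into confirmed responders. The documents give no value. At a true drug rate of 15%, the observed rate is p = 0.15 + 0.85s:

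| s (assumed) | p | P(early stop) | P(positive) |
|---|---|---|---|
| 0 | 0.150 | 0.492 | 0.079 |
| 5% | 0.1925 | 0.345 | 0.196 |
| 10% | 0.235 | 0.230 | 0.358 |
| 20% | 0.320 | 0.089 | 0.694 |

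With no drug effect at all, p = s, and P(positive) is 0.014 at 10%, 0.079 at 15% and 0.222 at 20%. The stated 8% is then exceeded only if surgery alone gives confirmed responses in more than about 15% of patients.

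**5. Existing safeguards.** Appendix A records affected sites, treated sites, residual papilloma and days since last surgery. The response rule uses none of the surgical items. The protocol also says "To ensure protocol compliance and consistency among participating sites, a Rapid Review will be conducted"; this covers each institution's first three cases and gives no rule for debrided sites.

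**The case against.** Several points on the other side stand.

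- Surgery is conditional. The operative visit is scheduled, but debridement depends on obstruction or the surgeon's judgement, and the Appendix A form has a box for waived surgery.
- Appendix A lists affected sites separately from treated sites and residual papilloma, which suggests that operating-room scores precede removal. The clinic scores still follow it.
- Endoscopic videos go to the Coordinating Center every 4 cycles and score sheets in real time, with no limit to the first three cases. That gives central visibility of operated cases, but no rule for classifying them.
- Appendix G (the CRFs) is not visible, so a convention there cannot be excluded. None appears in the endpoint text, Section 14.1 or Appendix A.
- The conversion shares are assumptions and regrowth erodes the effect.

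A reader might go further and infer that the ORR cannot be attributed to pembrolizumab at all. The documents do not support that: airway debridement does not affect RECIST responses, and clinical responses confirmed before any debridement are free of it. A reader might also infer that PR has no usable reference score. Baseline is the natural reading, given the pre-treatment mapping and the baseline visit on the form, and CR needs no reference. Not naming it is a minor gap.

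**Conclusion.** The concern holds. Followed exactly, the clinical rule can credit surgical removal to the drug in the count that decides a single-arm trial, and nothing visible in the plan prevents it. This is a defect in the primary endpoint definition and should be fixed before the ORR is analysed.

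Its size cannot be derived from the documents. The 19.6% and 35.8% rest on assumed conversion shares of 5% and 10% on top of a genuine 15% drug response rate; they illustrate sensitivity and do not estimate this trial's error rate. If the drug does nothing, surgery would have to give confirmed responses in more than about 15% of patients before the stated 8% is exceeded. The plan's operating characteristics are correctly computed, and they hold if surgical falls cannot count.

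**What to change.** In Sections 4.2.3.1, 10.1.2.6.1 and 14.1:

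1. State that the CR/PR reference is the pre-treatment baseline score and that operating-room scores are taken before tissue removal. Baseline endoscopy may be up to 6 weeks before enrollment (Section 9.1, footnote 21), and Section 5.1.3 does not treat endoscopic debridement as major surgery. So any site debrided at or after that endoscopy and before the first dose should be treated as debrided.
2. For the primary ORR, a fall at a debrided major site may not establish or confirm CR/PR on clinic scores taken after that debridement. It counts only on operating-room scores taken before removal. The text should acknowledge that some surgical effect can remain at 12 weeks: if regrowth were linear over an assumed 26 weeks, 1 − 12/26 = 54% of the fall would remain; over 12 weeks, none.
3. Pre-specify one sensitivity analysis: ORR counting only responses first documented and confirmed before any debridement at or after the baseline endoscopy.

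The Appendix A score per day since last surgery should be descriptive at most. If surgery is waived, an unchanged score of 20 gives 20/84 = 0.238 per day and later 20/168 = 0.119, an apparent halving with no clinical change.

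The cost is endpoint and SAP text and a scoring instruction. Responses may be dated later, and the stage-1 read-out may be later. Power falls if true responders are lost: at a 38% rate, losing 10% gives 0.38 × 0.90 = 0.342 and power 76.3%; losing 20% gives 0.304 and 63.7%.

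Sections 4.2.3.1, 7.1.2, 10.1.2.6 and 10.1.2.6.1, which tie treatment discontinuation to clinical progression, should be reconciled with the analysis definition; no clinical rule is proposed here. Separately, Appendix A scores the carina for SA and LO but omits it from the site lists (0 to 5 sites against 6 in the text), a minor form correction.
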